1. OBJECTIVES

To test the preliminary efficacy of a single dose of oral cannabidiol (CBD) in reducing anticipatory anxiety in patients with advanced cancer poised to undergo computed tomography (CT) scan or positron emission tomography (PET) to assess tumor burden.

Hypotheses

A single dose of oral cannabidiol is superior to placebo in reducing anticipatory anxiety in advanced stage cancer patients with pre-existing anxiety poised to undergo CT or PET to assess tumor burden.

1.1 Study Design

Randomized, double-blind, placebo-controlled trial of a single dose of CBD for anticipatory anxiety in advanced cancer patients.

1.1 Primary Objectives

In patients with advanced cancer poised to undergo CT or PET to assess tumor burden, to evaluate the preliminary efficacy of oral CBD, as compared to placebo, in reducing anticipatory anxiety as measured by the “Afraid” subscale of the Visual Analog Mood Scale (VAMS).

1.2 Secondary Objectives

To assess, using the Patient-Reported Outcomes version of the Common Terminology Criteria for Adverse Events (PRO-CTCAE™) and a qualitative assessment, patient-reported side effects and acceptability of taking oral CBD (versus placebo) for managing anticipatory anxiety.

To evaluate whether CBD is superior to placebo in improving mood (as measured by VAMS subscales), nausea (as measured by the European Organisation for Research and Treatment of Cancer core quality of life questionnaire-nausea subscale) and pain levels (as measured by the Numeric Pain Rating Scale [NPRS]) 3(+/-1) hours after study agent administration in patients with advanced cancer.

2. BACKGROUND

2.1 Study Disease(s)

Advanced breast cancer (stage IV or metastatic)

2.2 IND Agent

The IND agent, cannabidiol (Epidiolex), is manufactured by GW Pharmaceuticals and is Federal Drug Administration (FDA)-approved for management of seizures associated with some form of

pediatric epilepsy in patients 2-years of age or older.¹ Cannabidiol (Epidiolex) is a solution intended for oral consumption that contains, in addition to CBD (100 mg/mL), the following inactive ingredients: sesame seed oil, sucralose, alcohol and strawberry flavor.

Cannabidiol (C₂₁H₃₀O₂; molecular weight=314.46) is a non-intoxicating, non-addictive cannabis ingredient. A single clinical trial has been carried out in an oncology population. In this single-arm phase II trial targeting graft-versus-host disease prophylaxis, CBD was found to be safe for use (and of promising effectiveness) in patients undergoing allogeneic hematopoietic cell transplantation². Preclinical and clinical studies suggest that CBD possesses a variety of other therapeutic benefits with potential relevance to cancer patients. These include anxiolytic, antipsychotic, sedative, anticonvulsive, antiemetic, analgesic, and antitumor effects³⁻⁶. Zeroing in on evidence regarding anxiolysis, using a cross-over model, Crippa et. al. demonstrated through subjective report, physiological parameter testing, and functional neuroimaging that CBD significantly ameliorates reactive anxiety in healthy normals (2004; N=10; anxiety provoking stimulus: MRI), those with generalized social anxiety disorder (2011; N=10), and those with social phobia N= 30⁷. Although the agent's mechanism of action has yet to be fully elucidated, 5HT_{1A} receptor agonism is postulated to mediate such anti-anxiety effects^{5,7}.

In all human studies (including these), CBD is well-tolerated and, despite existing in the same plant as delta-9-tetrahydrocannabinol, manifests divergent and sometimes opposing effects^{3,5}. For instance, in sharp contrast to delta-9-tetrahydrocannabinol, CBD does not trigger abuse, dependence or withdrawal in preclinical studies. According to Epidiolex's package insert, its most common adverse reactions-- based on chronic twice-daily dosing-- include somnolence, decreased appetite, diarrhea, fatigue, malaise, asthenia, rash, insomnia, sleep disorder, poor quality sleep, infection, and dose-related transaminase elevations. When they occur, transaminase elevations typically present in the first two months of use of the drug, and mainly in patients on concomitant valproate. In a third of patients, the transaminase elevations improve without intervention. In two-thirds, the transaminase elevations respond to reduction or discontinuation of CBD, valproate, or both. Like all antiepileptic drugs, CBD carries a warning to monitor for suicidal behavior; however, clinical data from the pediatric trials does not seem to demonstrate increase in suicidal behavior compared to patients on placebo. Epidiolex's recent FDA approval, coupled with the United States Drug Enforcement Administration's (DEA) descheduling, has opened doors to clinical trials of CBD in oncology.

Preclinical models have demonstrated CBD to have a U-shaped dose response curve with respect to anxiety, with higher doses (20 or 100 mg/kg) ineffective and lower dose CBD (10 mg/kg) effective⁵. In humans, 300-600 mg doses were found to have anxiolytic effects⁸. According to the Epidiolex package insert, CBD "demonstrate[s] an increase in exposure that [is] less than dose-proportional over the range of 5 to 20 mg/kg/day." Cannabidiol has a time to maximum plasma concentration (T_{max}) of 2.5-5 hours at steady state. The effects of food are significant: Taking CBD in the setting of a caloric, high-fat meal increases the C_{max} 5-fold and the area under the curve (AUC) 4-fold. It also reduces the total variability, compared to the fasting state, in healthy volunteers. Cannabidiol's volume of distribution in healthy volunteers is 20,963 L to 42,849 L. Protein binding of the drug and its metabolites is >94% in vitro. The half-life of CBD in the plasma is 56-61 hours after a week of twice-daily dosing in healthy volunteers. Plasma clearance following a single 1500 mg CBD dose is 1111 L/h. Cannabidiol is metabolized by

CYP3A4 and CYP2C19. In the presence of moderate or strong inhibitors of these enzymes, dose reductions of CBD should be considered; in the presence of strong inducers, dose increases of CBD should be considered. Cannabidiol impedes metabolism of substrates of UGT1A9, UGT2B7, CYP2C8, CYP2C9, CYP2C19, and to an extent, CYP1A2 and CYP2B6. The somnolence and sedation experienced with CBD may be compounded by other central nervous system depressants such as alcohol or benzodiazepines. Of note, CBD is excreted in the feces with only mild renal clearance.

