2.3 Rationale

In the last half century, there have been few advances in the pharmacologic management of acute anxiety. As one example, a panic attack in 2019 is managed as it was in 1969: with a class of medications called benzodiazepines. While effective, benzodiazepines carry hefty risk profiles that include, acutely, cognitive slowing, even frank confusion, hypersomnia, perceptual disturbances, anterograde amnesia, accidental overdose, ataxia and hypotension, leading to falls and other injuries. Long-term benzodiazepine use may result in dependence, abuse, and a withdrawal reaction upon discontinuation.

The lack of pharmacologic innovation in the management of acute anxiety is particularly concerning to oncology, where anxiety is ubiquitous. According to one study, 42% of cancer patients manifest clinical anxiety after cancer diagnosis⁹. Cancer-related concerns are myriad and include health and existential anxieties (for instance, after receipt of alarming test results), psychosocial worries (for instance, around the impact of cancer on occupation and family), and fears regarding procedures (for instance, chemotherapy infusions, surgeries and scans to assess tumor burden). Of note, the anxiety tied to radiographic procedures to assess tumor burden peaks prior to the actual scan (rather than during or after).^{10,11} While management strategies include relaxation techniques, psychological treatments such as counseling, and antidepressants, the mainstay of treatment for moderate to severe acute cancer-related anxiety remains benzodiazepines. Although rates of benzodiazepine use among cancer patients have not been published in the last three decades, previously published rates range from 16-25%¹². We suspect that current rates are higher, first because prescription benzodiazepine use is on the rise in the United States¹³ and, second, because the National Comprehensive Cancer Network now identifies benzodiazepines among the chief management strategies for anticipatory nausea and vomiting with chemotherapy¹⁴. Of note, the DFCI website prominently encourages use of benzodiazepines prior to radiographic imaging¹⁵.

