Common, however, is not necessarily good. The risks attending benzodiazepine use can be magnified in cancer patients who are more likely to be frail and elderly. In addition, benzodiazepine use prior to an oncology appointment in which important medical information is to be transmitted may impair patient comprehension and decision-making ability. In the general public and, especially, in cancer populations, safer, effective alternatives to benzodiazepines are warranted.

Cannabidiol, a non-intoxicating, non-addictive cannabis ingredient, may confer similar benefits to benzodiazepines with fewer risks^{7,16}. Preclinical and clinical studies suggest that CBD possesses anxiolytic, antipsychotic, sedative, anticonvulsive, antiemetic, anti-inflammatory,

analgesic, and antitumor effects³⁻⁶. For instance, using a cross-over model, Crippa et. al. demonstrated through subjective report, physiological parameter testing, and functional neuroimaging that CBD significantly ameliorates reactive anxiety in healthy normals (2004; N=10; anxiety provoking stimulus: MRI), those with generalized social anxiety disorder (2011; n=10), and those with social phobia;⁷ n=30). Although the biochemical mechanism of cannabidiol has not yet been fully elucidated, 5HT_{1A} receptors in limbic and paralimbic areas are postulated to mediate its anxiolytic effects⁷.

In all human studies (including these), CBD was well-tolerated and, despite existing in the same plant as tetrahydrocannabinol, seems to have different and sometimes opposing effects to it^{3,5}. Administered acutely across a wide variety of oral (15 mg to 600 mg), intravenous (5 to 30 mg) and inhaled (0.15 mg/kg) doses, CBD produced no notable emotional, cognitive, psychomotor or vital sign side-effects⁷. Similarly, neither chronic administration up to 300 mg orally for 4.5 months (n=15) nor, in a case report, 1500 mg/day for four weeks produced notable side-effects^{17,18}. In the case of the former, neurological and physical examinations, blood and urine analyses, electrocardiograms and electroencephalograms were performed at regular intervals. In fact, the United States Food and Drug Administration (FDA) recently approved pharmaceutical-grade CBD manufactured by GW Pharmaceuticals under the trade name Epidiolex for management of forms of pediatric epilepsy. This approval, coupled with the United States Drug Enforcement Agency (DEA) rescheduling of it has opened the door more widely to clinical trials of CBD in oncology.

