3. PARTICIPANT SELECTION

3.1 Eligibility Criteria

3.1.1 Diagnosis of Stage IV or metastatic breast cancer

3.1.2 Age \geq 18 years.

3.1.3 Karnofsky \geq 60%.

3.1.4 Participants must have adequate organ and marrow function at baseline as defined below:

- total bilirubin \leq 2 times institutional upper limit of normal (ULN)
- AST(SGOT)/ALT(SGPT) \leq 3 \times institutional ULN

3.1.5 Baseline at least mild anxiety as measured by GAD-7 \geq 5

3.1.6 Experience of at least mild anxiety typically tied to anticipation of oncologic scans (as measured by a prescreen survey item)

3.1.7 Computed tomography or positron emission tomography (PET) to assess tumor burden scheduled for within 48 hours of study drug administration

3.1.8 No cannabis, delta-9-tetrahydrocannabinol or cannabidiol use within 24-hours of study drug administration.

3.1.9 No benzodiazepine consumption within 8 hours of study drug administration (e.g., nighttime benzodiazepine use permissible)

3.1.10 No driving for 12 hours following study drug administration.

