Once inclusion criteria have been met and exclusions ruled out, study staff will follow the registering processes described in Section 4.0. Participants will be randomized in a 2:1 fashion to CBD or placebo using permuted blocks within strata and a double-blind procedure will be followed. Randomization will be completed by the Office of Data Quality (ODQ). The eligibility checklist(s) and all pages of the consent form(s) will be faxed to the ODQ at [contact]. The ODQ will (a) review the eligibility checklist, (b) register the participant on the protocol, and (c) randomize the participant.

All survey assessments will be completed either in-person or remotely (either through RedCap, phone, text messaging or by mail).

Baseline: Following consent, if necessary (i.e., no such values exist in the chart within the last 6 weeks +/- 7 days), the patient will complete laboratory assessments, as well as a series of

surveys. If during the course of these assessments, the patient is determined to not meet eligibility criteria, they will be taken off study. Once the study team receives baseline assessment, the participant will be scheduled for Study Timepoint 1, which will take place within 48 hours of the anticipated CT scan or positron emission tomography (PET) to assess tumor burden. Study staff will follow up via phone, email, and/or mail to remind the study participant of the scheduled study visit.

Treatment Day:

The Treatment Day will take place within 48 hours of anticipated CT scan or positron emission tomography (PET) to assess tumor burden (based on the study participant's radiology appointment schedule). The study team will contact the participant approximately 24 hours before Timepoint 1 to ensure that the participant abstains from cannabis and benzodiazepine uses. Timepoint 1 (Pre-drug Administration Visit) will be completed prior to study drug administration. Observation for the drug administration is noted in section 5.3. Timepoint 2 (Post-drug Administration) will take place approximately 3(+/-1) hours following study drug administration. In total the treatment day inclusive of timepoint 1 and timepoint 2 will be approximately 8 hours(+/-1).

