Timepoint 1 (Pre-drug Administration): Regardless of randomization arm, all participants will complete a set of questionnaires. The study team will review questionnaire responses assessing cannabis and benzodiazepine uses (e.g. section 3.1.8 & 3.1.9 of the eligibility criteria). If a participant indicates they have consumed either within the prohibited timeframe, the study team will attempt to delay study drug administration in order to meet eligibility criteria. (Section 5 offers full details on consuming study drug). However, if the study drug administration cannot be delayed, the Treatment Day will be rescheduled to coincide with the next scheduled CT scan or positron emission tomography (PET). See section 8.1.11. for unused study drug destruction.

Timepoint 2 (Post-drug Administration): All participants will complete a set of questionnaires.

Timepoint 3: Study staff will phone the participant within a week +/- 7 days of study drug consumption to conduct a brief, semi-structured audio-recorded interview.

At study completion participants will receive a \$50 gift card. They will also receive up to \$50 for qualifying study-related travel costs and/or expenses. After all study procedures are completed, the research team will contact participants to inform of which arm they were assigned after unblinding and share any publications that come from this study.

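### Section 2.2 names alcohol as compounding CBD sedation, but the visible protocol has no instruction or question about alcoholic drinks: a modest gap that is cheap to close

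*Combined protocol and SAP*

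**What the plan says.** The pharmacology text in section 2.2 puts two depressants side by side: "The somnolence and sedation experienced with CBD may be compounded by other central nervous system depressants such as alcohol or benzodiazepines". Section 7.1.1 expects somnolence to be the likeliest adverse event of the single dose. It asks participants to refrain from benzodiazepines between study visits 2 and 3, and gives somnolence as the consequence of combining the two.

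The benzodiazepine side is then made operational:

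- Section 3.1.9: "No benzodiazepine consumption within 8 hours of study drug administration".
- Section 5.1.1 adds a contact about 24 hours before Timepoint 1 "to ensure that the participant abstains from cannabis and benzodiazepine uses".
- At Timepoint 1, under the same section: "The study team will review questionnaire responses assessing cannabis and benzodiazepine uses".

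The setting is described in sections 5.1.2 and 5.3. Participants take the dose themselves, on or off campus, and nobody observes them afterwards.

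The plan also has general precautions. Section 3.1.10 requires "No driving for 12 hours following study drug administration", and sections 5.3 and 5.3.2 set a 12-hour limit on operating machinery. Section 5.4 has a physician review the medication list before dosing. Section 7.3.2 keeps adverse events reportable for 30 days.

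**The concern.** The plan identifies a hazard with two named sources and gives participants an instruction about only one of them. The somnolence reasoning in section 7.1.1 applies just as well to alcohol, which section 2.2 names in the same sentence. A participant at home after an unobserved dose could drink that evening without departing from anything in the visible protocol.

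Two things are at stake, both small. The first is participant safety. The second is attribution. Sections 7 and 7.2 ask the investigator to judge whether an event is related to study treatment, and section 11.1 justifies the 2:1 allocation partly by the wish to assess side effects better. Whether and when a drowsy participant drank is a fact that this judgment needs, and no visible procedure collects it.

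**Working it through.** The plan states no figure on this point, so the check compares sections.

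**1. Where alcohol appears.** The supplied text mentions it five times: once as the interaction in section 2.2, and four times as a product ingredient (section 2.2 and 8.1.2 for Epidiolex; 5.1.2 and 8.2.1 for the vanilla extract in the placebo syrup). 1 + 4 = 5. None is a rule or question about drinking.

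**2. Which substance rules exist around dosing.** There are three separate ones: the cannabis limit (3.1.8), the benzodiazepine limit (3.1.9) and the benzodiazepine request (7.1.1). The 24-hour contact and the Timepoint 1 review put the first two into practice, so they are not further independent rules. Of the three, only 7.1.1 is tied to somnolence. The limit in 3.1.8 may be about overlapping exposure. The one in 3.1.9 may protect the endpoint, because section 2.3 says that "the mainstay of treatment for moderate to severe acute cancer-related anxiety remains benzodiazepines". The parallel with alcohol therefore rests on 7.1.1 read with 2.2.

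**3. What the calendar in section 9 records.** It has rows for concurrent medications and cannabis history, and none for alcohol.

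**4. How the timing falls.** The last scheduled adverse-event evaluation is at Timepoint 2, 3 (+/-1) hours after ingestion, which is 2 to 4 hours. The driving limit runs for 12 hours. So 12 - 4 = 8 to 12 - 2 = 10 hours of the period that the plan itself treats as needing caution come after that evaluation. Events can still be reported later, and Timepoint 3 includes an interview.

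**5. How many are exposed.** With 2:1 allocation of 50, 50 x 2/3 = 33.3 would receive CBD and 50 x 1/3 = 16.7 placebo. Without a drinking rate or a single-dose somnolence rate, no expected number of events follows.

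**6. How large the hazard is likely to be.** Section 2.3 reports that over acute oral doses of 15 to 600 mg "CBD produced no notable emotional, cognitive, psychomotor or vital sign side-effects"; since 15 <= 400 <= 600, the trial dose lies inside that range. The package-insert listing in section 2.2 describes a different exposure: "its most common adverse reactions-- based on chronic twice-daily dosing-- include somnolence". Both point to a modest risk. Neither statement describes CBD taken together with alcohol.

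**The case against.** The strongest objection is that the missing text may exist. Advice on drinking belongs naturally in the consent form, participant instructions or questionnaires, and none of these is in the supplied text. This stands as a limit on the claim: the gap is shown only for the protocol body and calendar.

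A reader might infer that the plan restricts and asks about nothing except cannabis and benzodiazepines. It does more. Sections 3.2.2 and 3.2.4 exclude clobazam, valproic acid and antiretroviral use, sections 5.1.2 and 5.3 limit food and some drinks, and section 5.4 and the calendar cover medication. None of these reaches alcoholic drinks.

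A reader might also count every substance check as a separate omission, or point to the avoid-list that names soft drinks and juices. Neither inference is supported. Two of the checks only enforce 3.1.8 and 3.1.9, and the food list concerns meals, which section 2.2 links to absorption rather than sedation.

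The window in 7.1.1 is unclear. The current schedule has a baseline and Timepoints 1 to 3, so visits 2 and 3 could mean dosing to Timepoint 2 (about 3 hours) or a longer span. On the shorter reading, a 12-hour alcohol instruction goes further than the benzodiazepine request. Its length is therefore better justified by the 12-hour driving limit.

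Finally, an investigator can ask about alcohol whenever somnolence is reported. That is true, but it depends on individual initiative and reaches only those who report an event.

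**Conclusion.** The point holds as a cheap improvement. In the visible protocol, a depressant that section 2.2 names as compounding CBD sedation has no instruction and no question attached, around a self-administered and unobserved dose that may be taken off campus. The risk is modest: a single 400 mg dose, with 12-hour driving and machinery limits that mitigate part of it.

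A reader might infer that the primary result is threatened. The documents do not support that. They give no drinking rate, and under randomization and intact blinding, drinking between Timepoints 1 and 2 would mainly add noise to the change score rather than favour an arm. No planned figure changes.

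The conclusion assumes that the unseen consent form and questionnaires do not already deal with alcohol. If they do, only the protocol wording needs aligning.

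**What to change.** - In sections 5.3, 5.3.2 and 7.1.1, instruct participants in both arms to avoid alcoholic drinks on the treatment day before dosing and for 12 hours after it, matching the driving limit. Say alcoholic drinks rather than alcohol, because both study products contain alcohol as an ingredient.
- Name alcohol in the existing contact about 24 hours before Timepoint 1.
- Record alcohol use and timing at Timepoint 2, covering the treatment day so far, and at the Timepoint 3 call, covering the rest of the 12 hours. The call may come up to 7 + 7 = 14 days after dosing, so recall will be imperfect.
- Use the answers only for adverse-event attribution and description, with no exclusion from the intent-to-treat analysis.

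Add no dose-delay or rescheduling rule for alcohol. A delay after the Timepoint 1 questionnaires would leave the pre-dose VAMS out of date. Rescheduling could waste a syringe that keeps for only 24 hours (8.1.3, 8.2.3) and cost patients when the attrition allowance is 50 - 45 = 5 (11.2).

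The cost is one added instruction and one or two added questions at existing contacts. Sample size and analysis stay as planned.
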